#### **Screening**

All screening evaluations to determine eligibility must be completed and reviewed by the individual providing medical supervision or Principal Investigator prior to study start. Generally, all labs to assess entry criteria must be completed no less than 10 days before subject enters study. Screening evaluations are outlined in **Figure 1**.

### **6.2.2 Enrollment, Baseline, and/or Randomization**

#### **Enrollment and Baseline Assessments**

All subjects will undergo an outpatient screening evaluation to assess their eligibility prior to entrance into the study. After informed consent, the following procedures will be conducted:

- A complete medical history and physical examination will be performed.
- Blood samples will be taken for a complete blood chemistry, blood counts, thyroid hormone panel and urinalysis.
- Subjects with diabetes will be excluded.
- Subjects will be assessed for dietary intake data and instructed on weight maintenance diets.

#### **Baseline Assessments**

See above combined Enrollment and Baseline Assessments section

#### **Randomization**

After completing initial physiological sequence, each subject will be randomized by [name] (study biostatistician). Subjects will be randomized to the 5011-Nutrasorb or placebo. The 5011-Nutrasorb used in human studies will be standardized using QA/QC concentration parameters established by the Botanical Core.

### **6.2.3 Blinding/Unblinding**

[name], Botanical Research Center biostatistician, will be responsible for all blinding procedures and for randomization. Randomization will be blinded to the staff performing the physical measures, metabolic testing, performance of assays, entering or calculating data related to the study and study investigators to assure minimal potential sources of bias. Sealed

randomization envelopes will be sent to the pharmacist for emergency unblinding. The randomization envelopes will be maintained in a secure location with access limited to authorized personnel.

Blinding is critical to the integrity of this clinical trial. However, in the event of a medical emergency or pregnancy in an individual subject, in which knowledge of the investigational product is critical to the subject's management, the blind for that subject may be broken by the medical investigator of the trial. This will be done by a request to the pharmacist to break the blind and report the treatment assignment to the medical investigator.

Before breaking the blind of an individual subject's treatment, the investigator should have determined that the information is necessary, i.e., that it will alter the subjects' immediate management. In many cases, particularly when the emergency is clearly not investigational product-related, the problem may be properly managed by assuming that the subject is receiving active product without the need for unblinding.

In case of an emergency, the investigator may open the emergency unblinding envelope to reveal the identity of the medication for that subject. If such unblinding occurs, the investigator shall notify the DSMB, NCCAM and IRB immediately. This information, including the reason for the blind being broken must be recorded in the participant chart and regulatory files.

#### **6.2.4 Follow-up Visits**

Follow-up visits will occur as outlined in **Figures 1 and 2**

#### **6.2.5 Completion/Final Evaluation**

Study design for both single and multiple dose studies are listed in detail in **Figures 1 and 2**

### **7. SAFETY ASSESSMENTS**

#### **7.1 Specification of Safety Parameters**

The plant has been used as a medicinal botanical or food for centuries and continues to be cultivated in Europe. PMI-5011 has been the primary study focus of our NIH Botanical Research Center since 2005 and a study focus at Rutgers University for at least 10 additional years. Extensive safety testing has been conducted with the botanical extract including complete Ames analysis, a 14-day repeated-dose oral toxicity study in rats and an oral subchronic 90-day toxicity study in rats, none of which showed any indication of toxicity.

#### **7.2 Methods and Timing for Assessing, Recording, and Analyzing Safety Parameters**

The study team including coordinator and investigators will inquire regarding adverse events while minimizing the chance for bias when detecting AEs and/or SAEs. The study team will employ open-ended and non-leading verbal questioning of the subject as the preferred method to inquire about AE occurrence. For examples, appropriate questions include: "How are you feeling?", "Have you had any (other) medical problems since your last visit/contact?", or "Have

you taken any new medicines, other than those provided in this study, since your last visit/contact?".

### **Recording of AEs and SAEs**

It is the responsibility of the investigator to review all documentation (e.g., hospital progress notes, laboratory, and diagnostics reports) relative to the event when an AE/SAE occurs. The investigator will then record all relevant information regarding an AE/SAE in the appropriate data collection tool.

We define an **adverse event (AE)** as any unfavorable and unintended diagnosis, symptom, sign (including an abnormal laboratory finding), syndrome or disease which either occurs during the study, having been absent at baseline, or if present at baseline, appears to worsen. Adverse events are to be recorded regardless of their relationship to the study intervention.

We will define a **serious adverse event (SAE)** as any untoward medical occurrence that results in death, is life threatening, requires inpatient hospitalization or prolongation of existing hospitalization, results in persistent or significant disability/incapacity, or in a congenital anomaly.

It is the responsibility of the investigator to attempt to establish a diagnosis of the event based on signs, symptoms, and/or other clinical information. In such cases, the diagnosis will be documented as the AE/SAE and not the individual signs/symptoms.

### **Evaluating AEs and SAEs**

#### **Assessment of Intensity**

An assessment of intensity for each AE and SAE reported during the study will be provided by the investigator and the investigator will assign it to one of the following categories:

- Mild: An event that is easily tolerated by the subject, causing minimal discomfort and not interfering with everyday activities.
- Moderate: An event that is sufficiently discomforting to interfere with normal everyday activities.
- Severe: An event that prevents normal everyday activities.

An AE that is assessed as severe will not be confused with an SAE and both AEs and SAEs can be assessed as severe. Severe Adverse Event is a category utilized for rating the intensity of an event when it meets at least one of the pre-defined outcomes as described in the definition of an SAE.

#### **Assessment of Causality**

The investigator is obligated to assess the relationship between study treatment and the occurrence of each AE/SAE. A "reasonable possibility" is meant to convey that there are facts/evidence or arguments to suggest a causal relationship, rather than a relationship cannot

be ruled out. The investigator will use clinical judgment to determine the relationship. Alternative causes, such as natural history of the underlying diseases, concomitant therapy, other risk factors, and the temporal relationship of the event to the study treatment will be considered and investigated.

### **7.3 Adverse Events and Serious Adverse Events**

An AE is any untoward medical occurrence in a patient or clinical investigation subject, temporally associated with the use of a medicinal product, whether or not considered related to the medicinal product. We define AE as any unfavorable and unintended sign (including an abnormal laboratory finding), symptom, or disease (new or exacerbated) temporally associated with the use of a medicinal product.

Events meeting the definition of an AE include:

- Any abnormal laboratory test results (hematology, clinical chemistry, or urinalysis) or other safety assessments (e.g., ECGs, radiological scans, vital signs measurements), including those that worsen from baseline, and felt to be clinically significant in the medical and scientific judgment of the investigator.
- Exacerbation of a chronic or intermittent pre-existing condition including either an increase in frequency and/or intensity of the condition.
- New conditions detected or diagnosed after study treatment administration even though it may have been present prior to the start of the study.
- Signs, symptoms, or the clinical sequelae of a suspected interaction.
- Signs, symptoms, or the clinical sequelae of a suspected overdose of either study treatment or a concomitant medication (overdose per se will not be reported as an AE/SAE).

Events that do not meet the definition of an AE include:

- Any clinically significant abnormal laboratory findings or other abnormal safety assessments that are associated with the underlying disease, unless judged by the investigator to be more severe than expected for the subject's condition.
- The disease/disorder being studied, or expected progression, signs, or symptoms of the disease/disorder being studied, unless more severe than expected for the subject's condition.
- Medical or surgical procedure (e.g., endoscopy, appendectomy); the condition that leads to the procedure is an AE.
- Situations where an untoward medical occurrence did not occur (social and/or convenience admission to a hospital).
- Anticipated day-to-day fluctuations of pre-existing disease(s) or condition(s) present or detected at the start of the study that do not worsen.

## **Definition of Serious Adverse Events**

If an event is not an AE, then it cannot be an SAE even if serious conditions are met (e.g., hospitalization for signs/symptoms of the disease under study, death due to progression of disease, etc.).

An SAE is any untoward medical occurrence that, at any dose, results in death, is life-threatening, requires hospitalization or prolongation of existing hospitalization, results in disability/incapacity or a congenital anomaly/birth defect. We define an SAE as one associated with liver injury **and** impaired liver function defined as: ALT  $\square$  3xULN, and total bilirubin  $\square$  2xULN or INR  $> 1.5$ .

### **7.4 Reporting Procedures**

Once the investigator determines that an event meets the protocol definition of an SAE, the SAE will be reported to the IRB and Chair of Data Safety Monitoring Committee within 24 hours and notification will be sent to program official at NCCAM/ODS. If the investigator does not have all information regarding an SAE, the investigator will not wait to receive additional information before notifying the responsible parties of the event and completing the appropriate forms. An assessment of causality at the time of the initial report will be provided. Email transmission of the SAE data collection tool will be the preferred method to transmit this information followed by notification by telephone and/or fax. A copy of the SAE report will also be sent to the institution officials and via overnight mail to NCCAM/ODS officials. Initial notification via the telephone does not replace the need for the investigator to complete and sign the SAE data collection tool within the designated reporting time frames.

### **7.5 Follow-up for Adverse Events**

After the initial AE/SAE report is completed and sent, the investigator is required to proactively follow each subject at subsequent visits/contacts. As currently practiced, it is planned that all AEs and SAEs will be followed in clinic until: 1) resolution; 2) the condition stabilizes; 3) the event is otherwise explained; or 4) the subject is lost to follow-up.

Additional measurements and/or evaluations as may be indicated will be conducted by the investigator/research team in order to elucidate as fully as possible the nature and/or causality of the AE or SAE. These evaluations/measurements may include additional laboratory tests or investigations, histopathological examinations, consultation with other health care professionals or radiologic examinations. In the event that a subject dies during participation in the study or during a recognized follow-up period, the investigator will provide the IRB/DSMB with a copy of any post-mortem findings, including histopathology.

New or updated information will be recorded in the originally completed data collection tool. The investigator will submit any updated SAE data within the designated reporting time frames.

## 7.6 Safety Monitoring

As is required of all protocols conducted at Pennington Biomedical Research Center, Human Subjects research studies will undergo independent monitoring. Additional monitoring by NCCAM and ODS Program Officials will be expected to provide additional specific guidelines to the PI for the study.

## 8. INTERVENTION DISCONTINUATION

Subject Completion: A completed subject is one who has completed all phases of the study including the follow-up visit. The end of the study is defined as the last subject's last visit.

Subject Withdrawal Criteria: A subject may withdraw from study treatment at any time at his/her own request, or may be withdrawn at any time at the discretion of the investigator for safety, behavioral or administrative reasons.

### Subject Withdrawal Procedures

Subject Withdrawal from Study: Every effort will be made to follow-up subjects who withdraw or are withdrawn from the study prematurely.

- If a subject withdraws or is withdrawn from the study at a scheduled visit after dosing, complete assessments for the scheduled visit and any other assessments specified for the follow-up visit that are not included in the regularly scheduled visit, where possible.
- If a subject withdraws or is withdrawn from the study between visits after randomization, complete assessments for follow-up visit, where possible.
- At a minimum, the following assessments should be performed for any subject who is withdrawn from the study; clinical safety labs and AE assessment.

Subjects who terminate their participation due to adverse events should be followed up as appropriate in order to determine the final outcome.

Subject Withdrawal from Study Treatment: Subjects may withdraw from the study at any time and for any reason. They are not obliged to state the reason for withdrawal. However, the reasons for withdrawal, or failure to provide a reason, must be documented by the physician on the case report form.

Treatment After the End of the Study: Subjects will not receive any additional treatment after completion of the study because only healthy volunteers are eligible for study participation for the safety and tolerability studies and will not be on glucose lowering medication if they have obesity or insulin resistance.

Screen and Baseline Failures: Data for screen and baseline failures will be collected in source documentation at the site.

## 9. STATISTICAL CONSIDERATIONS

### 9.1 General Design Issues

The trials described in this protocol are the first stage of testing *Artemisia* sp. extract in humans. The studies will be conducted in (1) an ascending single dose evaluation of doses 0.3, 1, 3, 10, 20, and 30 g; and (2) a multiple oral dose evaluation of 3 doses chosen from the first evaluation and denoted doses 1, 2, and 3 as described in Section 3, Study Design. The single dose evaluation will be conducted by studying 6 doses (amounts) of extract and a placebo in a series of 3-treatment, 3-period crossover trials. The 3 treatments (placebo or one of two doses of extract) will be given at weekly intervals each in a single dose followed by a 7 day washout period. Each crossover trial will consist of 3 sequences of treatments across the weekly intervals [each sequence being a different order for receiving a triad of 2 doses of extract and a placebo (dose 1, dose 2, placebo; dose 3, dose 4, placebo; dose 5, dose 6, placebo)]. The placebo can be taken in period 1, period 2 or period 3 and the extract is taken in the other two periods where the lower dose of extract is always taken in a period that precedes that of the higher dose]. The primary objective is to assess the safety and tolerability of ascending amounts of the extract for each amount given in a single dose. If no adverse effects are observed with a given pair of extract doses, the dose escalates (e.g. dose 1, dose 2, placebo escalates to dose 3, dose 4, placebo which escalates to dose 5, dose 6, placebo) and a new cohort of subjects is studied in a new crossover trial with each escalation.

The multiple dose evaluation will be conducted similarly by studying 3 doses (amounts) of extract and a placebo in a series of 3-treatment, 3-period crossover trials. The 3 treatments (placebo or one of two doses of extract) will each be given once daily across a 21 day period followed by a 7 day washout period. Each crossover trial will consist of 3 sequences of treatment (each sequence being a different order for receiving 2 doses of extract and a placebo where the lower dose of extract always precedes the higher dose). The primary purpose is to further investigate safety, tolerability and bioavailability of once daily consumption of the extract over a 7 day period.

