### 3. STUDY DESIGN

#### A. Phase 1 Studies: Ascending Single Oral Dose Evaluation

**Objective:** The **primary objective** will be to assess the safety and tolerability of a single dose of the 5011-Nutrasorb in healthy subjects. Although this study is not designed to evaluate efficacy, we will assess the effect of a single dose of the botanical complex on glucose tolerance to determine if there is an acute effect.

**Subjects:** Twenty seven healthy subjects (3 cohorts of 9 subjects) who have passed all screening evaluations and have given informed consent will be recruited for the Phase I studies. Healthy subjects are defined as individuals who are free of significant cardiac, pulmonary, gastrointestinal, hepatic, renal, hematological, endocrine, neurological and psychiatric disease as determined by history, physical examination and clinical laboratory tests.

**Dosing:** A representative dosing schedule and randomization for this study is outlined in Table 1. We will begin dosing at very low doses based on the dose response data generated from the mice studies. Based on dosing considerations (see Section 5.1), the suggested dosing range would be 3-30 g subject. Thus, our suggested doses will be 0.3, 1, 3, 10, 20 and 30 g. We will use the same extract dose for all participants irrespective of their weight. Each subject will receive three single doses (two doses of 5011-Nutrasorb and one of placebo) separated by washout periods of at least 7 days. In each treatment period a single dose of extract will be administered on day 1. Up to 9 treatment sequences (3 sequences in each of 3 cohorts) are planned for the single dose evaluations (**Table 1**).

Table 1. Ascending Oral Dose Randomization			
	Period 1	Period 2	Period 3
COHORT 1			
Sequence 1 (n=3)	Dose 1	Dose 2	Placebo
Sequence 2 (n=3)	Dose 1	Placebo	Dose 2
Sequence 3 (n=3)	Placebo	Dose 1	Dose 2
COHORT 2			
Sequence 4 (n=3)	Dose 3	Dose 4	Placebo
Sequence 5 (n=3)	Dose 3	Placebo	Dose 4
Sequence 6 (n=3)	Placebo	Dose 3	Dose 4
COHORT 3			
Sequence 7 (n=3)	Dose 5	Dose 6	Placebo
Sequence 8 (n=3)	Dose 5	Placebo	Dose 6
Sequence 9 (n=3)	Placebo	Dose 5	Dose 6

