#### **Assessments and Evaluations:**

**Figure 2: Multiple Dose Study**

Day of Study	Scr	-3	1	3	7	10	14	17	21
Randomization			•						
Vital Signs/Body Weight	•	•	•	•	•	•	•	•	•
Complete Blood Chemistry	•				•		•		•
Physical Exam/EKG	•				•		•		•
OGTT		•			•		•		•
Plasma Metabolites					•		•		•
Insulin Secretory Assessment	•				•		•		•
Fasting Insulin/Glucose	•				•		•		•
Bioactives: Plasma/Excretion*					•		•		•
DXA		•							•
Adverse Event Assessment	•	•	•	•	•	•	•	•	•

**Figure 2: Proposed Study Design Assessing Multiple Dose Study for each Period.** There will be three study periods of assessment (see Table 2). SCR; Screening (only done in the first study period). A one day +/- visit window is allowed.

*\*NOTE Subjects will be given their intervention (low or high dose 5011-Nutrasorb or placebo) two hours prior to start of OGTT (0 hour) and will have plasma obtained at 0, 30 minutes, 1, 1.5, 2, 3, and 4 hours post ingestion. After initial void, urine will be collected over the 6 hour interval. These specimens will be measured in the Botanical Core lab. Note: Intervention will not be administered at Day -3 of each test period.*

**Baseline/Screening Evaluation:** All subjects will undergo an outpatient screening evaluation to assess their eligibility prior to entrance into the study. A complete medical history and physical examination will be performed. Blood samples will be taken for a complete blood chemistry, blood counts, thyroid hormone panel and urinalysis. Subjects with impaired glucose tolerance or diabetes will be excluded. During baseline, subjects will be assessed for dietary intake data and instructed on weight maintenance diets. A taste (small sip) of the study product will also be administered during screening.

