#### **9.6 Data Analyses**

Statistical comparisons will focus on comparisons between subjects randomized to the selected *Artemisia* sp. extract and the placebo group with respect to baseline to follow-up change in: (a) a descriptive summary of adverse events, complete hematologic and biochemistry profile in blood, and measures of glucose and insulin response to glucose tolerance will be compiled for both single and multiple dose studies; (b) measurements assessing lipid metabolism, i.e. fasting lipid profile; (c) physiologic assessments of insulin action (HOMA-IR) and insulin secretion; and (d) body weight/body composition. For each outcome, the equality of the outcome means for 5011-Nutrasorb versus placebo will be tested against a two-directional alternative, controlling the type 1 error at  $\alpha = 0.05$ . The analyses will be conducted using mixed effects linear statistical

models with repeated measures to conduct analysis of variance for crossover designs. Post-hoc tests will be conducted for pairwise comparisons of extract doses and placebo employing the Tukey method for controlling the global comparison-wise significance at 0.05 level. Logarithms or other transformations will be analyzed for data seriously deviating from normality; alternatively, non-parametric analyses may be conducted.

Handling of missing data: The data will be analyzed using the procedures PROC MIXED and PROC GLIMMIX SAS (v 9.3 or later). Thus, mixed effects models for repeated measures will be employed to analyze all available data irrespective of missing or incomplete data attributable to dropouts or other phenomena. Our experience in previous studies that employed similar study designs resulted in little if any missing data. Nevertheless, in anticipation of the possibility of such we plan to conduct sensitivity analyses that compare our findings against protocol completer analyses and last observation carried forward analyses in addition to investigating characteristics of participants who fail to protocol.

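### Section 9.6 analyses change from an undefined baseline; if that baseline is each period's Day -3, a raw change score loses precision and is exposed to any residual effect within the washout

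*Combined protocol and SAP*

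**What the plan says.** **Outcome metric.** Section 9.6 compares extract with "the placebo group with respect to baseline to follow-up change in" safety laboratory, lipid, insulin and body-composition measures. It uses a mixed-effects repeated-measures model for a crossover, with two-sided tests at 0.05. It names no baseline visit, baseline covariate or carry-over term.

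**Multiple-dose timing.** Section 9.1 says the treatments "will each be given once daily across a 21 day period followed by a 7 day washout period". Figure 2 is captioned "Proposed Study Design Assessing Multiple Dose Study for each Period", with "SCR; Screening (only done in the first study period). A one day +/- visit window is allowed". Its footnote adds that "Intervention will not be administered at Day -3 of each test period". The figure places an OGTT, a DXA and body weight on Day -3. Body weight is also taken on Day 1. Blood chemistry is drawn at screening and on Days 7, 14 and 21, and Section 3.B gives fasting lipids on Days 7, 14 and 21 only.

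**Single-dose timing.** Section 3.A has single doses "separated by washout periods of at least 7 days". An OGTT is done on Day -3 and on Day 1. The text describes Day -3 as coming before randomization, yet the Figure 1 caption applies the schedule to each period of Table 1.

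**Residual effect.** Section 3.A, after Table 1, promises an analysis of residual extract effect after washout but gives no method. Section 3.B has no counterpart for the multiple-dose study.

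**The concern.** Screening is confined to Period 1, so Day -3 is the only pre-dose OGTT and DXA scheduled in Periods 2 and 3. That makes it the natural baseline for those outcomes. Two consequences follow if it is subtracted.

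First, in a crossover the subject effect already removes stable differences between people. Subtracting a further within-period measurement adds that measurement's noise. Adjusting for it by regression uses the same information at the best weight.

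Second, Day -3 lies inside the plan's own washout. An effect of the previous treatment that persists to that day is subtracted from the next treatment's result. In Section 9.1 the lower dose always comes before the higher, so the sequences are not balanced for carry-over and such an effect does not average out.

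The cohorts are small (9 subjects each) and Section 9.2 gives no power calculation, so avoidable loss of precision matters. Section 3.B also allows glucose-tolerance results to prompt dose changes or an added cohort, so the dose contrasts may be acted upon.

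**Working it through.** There is no SD, power or variance figure in the documents to reproduce. r, the residual fraction L and the dose-response shapes below are assumptions, shown as ranges.

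**1. Timing (Section 9.1, Figure 2).**
- The last dose is on day 21, washout is days 22 to 28, and the next Day 1 is day 29.
- Counting a Day 0, Day -3 is day 25, which is 4 days after the last dose. Without a Day 0 it is day 26, or 5 days.
- The visit window of one day either way widens this to 3 to 6 days.
- In the single-dose study at minimum spacing, if Day -3 is repeated each period, it falls 3 to 5 days after the previous dose.

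**2. Precision.** Let s² be the within-subject variance, equal at Day -3 and follow-up. Let r be their within-period correlation after removing the subject effect.
- Change score: variance proportional to 2s²(1 - r).
- Follow-up with Day -3 as covariate: about s²(1 - r²).
- Ratio: 2(1 - r)/(1 - r²) = 2/(1 + r).

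| r | variance ratio | SE ratio |
|---|---|---|
| 0 | 2.00 | 1.41 |
| 0.3 | 1.54 | 1.24 |
| 0.5 | 1.33 | 1.15 |
| 0.7 | 1.18 | 1.08 |
| 0.9 | 1.05 | 1.03 |

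Against follow-up values with no baseline at all, the change-score ratio is 2(1 - r): 2.0 at r = 0, 1.0 at r = 0.5 and 0.5 at r = 0.75. So subtraction is worse than ignoring the baseline only below r = 0.5, but it is worse than adjusting for the baseline at every r below 1, apart from about one degree of freedom.

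The worst case is r = 0. For an assumed effect of one within-subject SD, power there is 25% (change) against 44% (follow-up) in one cohort with 14 df. Over three cohorts with 45 df it is 49% against 78%.

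**3. Bias if something remains on Day -3.** Let a fraction L of the previous treatment's effect be present on Day -3. The expected change score is then the current effect minus L times the previous effect. Least squares on the Table 3 sequences (subject, period-within-cohort and treatment effects), with all three true dose effects equal to 1.00, gives:

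| L | D1 | D2 | D3 | D3 - D1 |
|---|---|---|---|---|
| 0 | 1.00 | 1.00 | 1.00 | 0 |
| 0.10 | 1.06 | 1.03 | 1.01 | -0.04 |
| 0.25 | 1.14 | 1.08 | 1.03 | -0.11 |
| 0.50 | 1.28 | 1.17 | 1.06 | -0.22 |

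The pattern depends on the assumed shape. Across equal, ordinal (1/3, 2/3, 1) and linear-in-grams effects, D3 is overstated by 3-13% at L = 0.25 and 6-26% at L = 0.5. With period effects common to all cohorts the ranges are 3-11% and 6-21%.

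**4. What a covariate does to that bias.** The adjusted estimate subtracts b times the Day -3 contrast instead of 1 times it, so it carries about b times the bias above. With equal variances b is about r: at r = 0.5 the bias is roughly halved, not removed. Follow-up-only estimates at Day 21 stay within 0.5% of the truth over this range of L, assuming exponential decay of the residual effect.

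**The case against.** The strongest objection is to the premise. A reader might infer that the plan subtracts each period's Day -3 value, but Section 9.6 does not say so. Section 3.A describes Day -3 as preceding randomization, and Section 3.B mentions the Day -3 OGTT and a baseline DXA before it introduces the three periods. Either can be read as one study baseline. A single baseline is constant within subject, cancels from every within-subject contrast, and removes both problems. A repeated-measures model could also treat baseline as a response. This stands: the certain defect is that baseline is undefined, and the rest is conditional.

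Scope is also limited. Lipids and blood chemistry have no Day -3 sample in either study, and in the single-dose study neither does body weight. In Figure 2 the separate fasting insulin/glucose row is marked at screening and not on Day -3, although Section 3.B and the OGTT itself supply fasting values that day. The point therefore reaches OGTT-derived measures and, in the multiple-dose study, DXA and body weight.

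A reader might also infer that the precision loss is always large, or that the dose estimates will be biased. Neither follows. Body weight and DXA may well have r above 0.7, where the SE penalty is 8% or less. No document supports any particular L. The only persistence data (Section 6.2, mice) show no compound detectable at 24 hours. Those data concern plasma compounds and not metabolic effects after 21 days of dosing in humans, so they lessen the worry without settling it. The residual-effect analysis promised in Section 3.A answers part of the point for the single-dose study only.

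Finally, the primary outcome is safety and tolerability, its adverse-event summary is descriptive, and Section 9.2 disclaims power for efficacy.

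**Conclusion.** The point holds in conditional form. Section 9.6 leaves the baseline undefined, so an analyst could choose it after seeing data. If the period's Day -3 value is used, as Figure 2 implies for OGTT measures, DXA and body weight in the multiple-dose study (and for OGTT in the single-dose study if Figure 1 is repeated each period), a raw change score has a standard error 3% to 41% larger than the adjusted analysis for r between 0.9 and 0. This rests on equal variances at the two visits and on a correlation that the documents do not give, and it needs no carry-over.

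Bias is a separate possibility: zero if the effect has gone by Day -3, and otherwise dependent on the residual fraction and on the dose-response shape. The documents do not support a claim that bias will occur, or that all Section 9.6 outcomes are exposed. Because the outcomes affected are mainly secondary and the remedy uses data already collected, this is a free improvement and not a flaw that threatens the primary safety assessment.

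**What to change.** In Section 9.6:

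1. Name the baseline visit for each outcome and each study. Include those without a Day -3 sample, and body weight in the multiple-dose study, which has both Day -3 and Day 1 values.
2. Where a period Day -3 value exists, replace the change score by the on-treatment value: Days 7, 14 and 21 in the multiple-dose study (Day 21 for DXA), and the Day 1 OGTT in the single-dose study. Use the period's Day -3 value as a covariate, centred on the subject's own mean Day -3 value.
3. Repeat the analysis without the period baseline as a sensitivity analysis, because a contaminated covariate still passes on part of any bias.
4. Extend the residual-effect check of Section 3.A to the multiple-dose study and give its method: compare Day -3 values by preceding treatment, within Period 2 and within Period 3. Comparing those periods with Period 1 would confound a residual effect with a period effect. Under Table 3, each of Periods 2 and 3 has 18 subjects coming from extract and 9 from placebo, so report the estimate with its confidence interval; a non-significant test would not show absence.

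The cost is SAP wording and about one degree of freedom. No new visit or sample is needed.
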